## 7.4. Replacement of unusable vaccine doses

In addition to the vaccine doses provided for the planned number of subjects (including over-randomization when applicable), at least 10% additional vaccine doses will be supplied to replace those that are unusable.

The investigator will use SBIR to obtain the replacement vial number. The replacement numbers will be allocated by dose. The system will ensure, in a blinded manner, that the replacement vial matches the formulation the subject was assigned to by randomization.

## 7.5. Contraindications to subsequent vaccination

The following events constitute absolute contraindications to further administration of ChAd155-RSV. If any of these events occur during the study, the subject must not receive additional doses of vaccine but may continue other study procedures at the discretion of the investigator (see Section 9.5).

- Anaphylaxis following the administration of vaccines.
- Any confirmed or suspected immunosuppressive or immunodeficient condition, including HIV infection.
- Any condition that in the judgment of the investigator would make IM injection unsafe.
- Current autoimmune disease.
- Acute or chronic, clinically significant pulmonary, cardiovascular, hepatic or renal functional abnormality, as determined by physical examination or laboratory tests.
- Failure to thrive.

The following events constitute contraindications to administration of ChAd155-RSV at that point in time; if any of these events occur at the time scheduled for vaccination, the subject may be vaccinated at a later date, within the time window specified in the protocol (see Section 6.5), or the subject may be withdrawn at the discretion of the investigator (see Section 9.5).

- Acute disease and/or fever at the time of vaccination.
  - Fever is defined as temperature  $\geq 38.0^{\circ}\text{C} / 100.4^{\circ}\text{F}$ . The preferred location for measuring temperature in this study will be the axilla for subjects  $\geq 1$  and  $< 5$  years of age and the rectum for subjects  $< 12$  months of age.
  - Subjects with a minor illness (such as mild diarrhea, mild upper respiratory tract infections) without fever can be administered all vaccines.
  - Receipt of a routine pediatric vaccine within the previous 7 days, with the exception of live viral vaccines, for which an interval of 14 days should be respected.

## 7.6. Concomitant medications/products and concomitant vaccinations

At each study visit, the investigator or delegate should question the subject's parent(s)/LAR(s) about any medications/products taken and vaccinations received by the subject.

Scheduled routine pediatric vaccines may be administered  $\geq 7$  days before a dose of study vaccine or  $\geq 7$  days following a dose of study vaccine, with the exception of live viral vaccines which may be administered  $\geq 14$  days before a dose or  $\geq 7$  days after a dose. Vaccines needed for urgent individual medical need (e.g., rabies prophylaxis) may be administered at any time.

In case an emergency mass vaccination for an unforeseen public health threat (e.g., a pandemic) is organized by the public health authorities, outside the routine immunization program, the time period described above can be reduced if necessary for that vaccine provided it is licensed and used according to its Summary of Product Characteristics (SmPC) or Prescribing Information and according to the local governmental recommendations and provided a written approval of the Sponsor is obtained.

### **7.6.1. Recording of concomitant medications/products and concomitant vaccinations**

The following concomitant medication(s)/product(s)/vaccine(s) must be recorded in the eCRF.

- All concomitant medications/products, except vitamins and dietary supplements, administered in the 30 day follow-up period after the administration of each dose of study vaccines (Day 1 to Day 30).
- Any concomitant vaccination administered in the period starting 30 days before the first dose of study vaccines and ending at the last study visit (Day -29 to end of the second RSV transmission season).
- Prophylactic medication (i.e., medication administered in the absence of ANY symptom and in anticipation of a reaction to the vaccination or blood sampling).
  - E.g. an anti-pyretic is considered to be prophylactic when it is given in the absence of fever and any other symptom, to prevent fever from occurring (fever is defined as temperature  $\geq 38.0^{\circ}\text{C}/100.4^{\circ}\text{F}$  regardless the location of measurement). The preferred location for measuring temperature in this study will be the axilla for subjects  $\geq 1$  and  $< 5$  years of age and the rectum for subjects  $< 12$  months of age.
  - E.g. a topical local anesthetic used prior to a blood sampling is considered to be prophylactic.
- Any concomitant medications/products/vaccines listed in Section [7.6.2](#).
- Any concomitant medications/products/vaccines relevant to a SAE to be reported as per protocol or administered at any time during the study period for the treatment of a SAE. In addition, concomitant medications relevant to SAEs need to be recorded on the expedited Adverse Event report.
- Any antipyretic administered in the period starting 6 hours before vaccination and ending 12 hours after vaccination need to be recorded on the specific page of the eCRF.

### 7.6.2. Concomitant medications/products/vaccines that may lead to the elimination of a subject from per-protocol analyses

The use of the following concomitant medications/products/vaccines will not require withdrawal of the subject from the study but may determine a subject's evaluability in the per-protocol analysis. See Section 11.5 for cohorts to be analysed.

- Any investigational or non-registered product (drug or vaccine) other than the study vaccines used during the study period.
- Immunosuppressants or other immune-modifying drugs administered chronically (i.e., more than 14 days in total) during the study period. For corticosteroids, this will mean prednisone  $\geq 0.5$  mg/kg/day (for pediatric subjects), or equivalent. Inhaled and topical steroids are allowed.
- Long-acting immune-modifying drugs administered at any time during the study period (e.g., infliximab).
- A vaccine not foreseen by the study protocol administered during the period starting 30 days before the first dose and ending 30 days after the last dose of vaccine\*, with the exception of:
  - Scheduled routine pediatric vaccines which may be administered  $\geq 7$  days before a dose and  $\geq 7$  days after a dose of study vaccines, with the exception of live viral vaccines which may be administered  $\geq 14$  days before a dose or  $\geq 7$  days after a dose.
  - Vaccines needed for urgent individual medical need (e.g., rabies prophylaxis).

\*In case an emergency mass vaccination for an unforeseen public health threat (e.g.: a pandemic) is organized by the public health authorities, outside the routine immunization program, the time period described above can be reduced if necessary for that vaccine provided it is licensed and used according to its Summary of Product Characteristics (SmPC) or Prescribing Information and according to the local governmental recommendations and provided a written approval of the Sponsor is obtained.

- Immunoglobulins and/or any blood products administered during the study period.

## 8. HEALTH ECONOMICS

Not applicable.

## 9. SAFETY

The investigator or site staff is/are responsible for the detection, documentation and reporting of events meeting the criteria and definition of an AE or SAE as provided in this protocol.

Each subject's parent(s)/LAR(s) will be instructed to contact the investigator immediately should they/the subject manifest any signs or symptoms they perceive as serious.

## 9.1. Safety definitions

### 9.1.1. Definition of an adverse event

An AE is any untoward medical occurrence in a clinical investigation subject, temporally associated with the use of a medicinal product, whether or not considered related to the medicinal product.

An AE can therefore be any unfavourable and unintended sign (including an abnormal laboratory finding), symptom, or disease (new or exacerbated) temporally associated with the use of a medicinal product. For marketed medicinal products, this also includes failure to produce expected benefits (i.e., lack of efficacy), abuse or misuse.

Examples of an AE include:

- Significant or unexpected worsening or exacerbation of the condition/indication under study.
- Exacerbation of a chronic or intermittent pre-existing condition including either an increase in frequency and/or intensity of the condition.
- New conditions detected or diagnosed after study vaccines administration even though they may have been present prior to the start of the study.
- Signs, symptoms, or the clinical sequelae of a suspected interaction.
- Signs, symptoms, or the clinical sequelae of a suspected overdose of either study vaccines or a concurrent medication (overdose per se should not be reported as an AE/SAE).
- Signs, symptoms temporally associated with study vaccines administration.
- Pre- or post-treatment events that occur as a result of protocol-mandated procedures (i.e., invasive procedures, modification of subject's previous therapeutic regimen).

AEs to be recorded as endpoints (solicited AEs) are described in Section 9.1.3. All other AEs will be recorded as UNSOLICITED AEs.

Examples of an AE DO NOT include:

- Medical or surgical procedures (e.g., endoscopy, appendectomy); the condition that leads to the procedure is an AE/SAE.
- Situations where an untoward medical occurrence did not occur (e.g., social and/or convenience admission to a hospital, admission for routine examination).
- Anticipated day-to-day fluctuations of pre-existing disease(s) or condition(s) present or detected at the start of the study that do not worsen.
- Pre-existing conditions or signs and/or symptoms present in a subject prior to the first study vaccination. These events will be recorded in the medical history section of the eCRF.

### 9.1.2. Definition of a serious adverse event

A SAE is any untoward medical occurrence that:

- a. Results in death,
- b. Is life-threatening,

Note: The term 'life-threatening' in the definition of 'serious' refers to an event in which the subject was at risk of death at the time of the event. It does not refer to an event, which hypothetically might have caused death, had it been more severe.

- c. Requires hospitalization or prolongation of existing hospitalization,

Note: In general, hospitalization signifies that the subject has been admitted at the hospital or emergency ward for observation and/or treatment that would not have been appropriate in the physician's office or in an out-patient setting. Complications that occur during hospitalization are also considered AEs. If a complication prolongs hospitalization or fulfills any other serious criteria, the event will also be considered serious. When in doubt as to whether 'hospitalization' occurred or was necessary, the AE should be considered serious.

Hospitalization for elective treatment of a pre-existing condition (known or diagnosed prior to informed consent signature) that did not worsen from baseline is NOT considered an AE.

- d. Results in disability/incapacity,

Note: The term disability means a substantial disruption of a person's ability to conduct normal life functions. This definition is not intended to include experiences of relatively minor medical significance such as uncomplicated headache, nausea, vomiting, diarrhea, influenza like illness, and accidental trauma (e.g., sprained ankle) which may interfere or prevent everyday life functions but do not constitute a substantial disruption.

Medical or scientific judgement should be exercised in deciding whether reporting is appropriate in other situations, such as important medical events that may not be immediately life-threatening or result in death or hospitalization but may jeopardise the subject or may require medical or surgical intervention to prevent one of the other outcomes listed in the above definition. These should also be considered serious.

Examples of such events are invasive or malignant cancers, intensive treatment in an emergency room or at home for allergic bronchospasm, blood dyscrasias or convulsions that do not result in hospitalization.

### 9.1.3. **Solicited adverse events**

#### 9.1.3.1. **Solicited local (injection-site) adverse events**

The following local (injection-site) AEs will be solicited:

**Table 17      Solicited local adverse events**

All age groups
Pain at injection site
Redness at injection site
Swelling at injection site

#### 9.1.3.2. **Solicited general adverse events**

The following general AEs will be solicited:

**Table 18      Solicited general adverse events**

Infant
Drowsiness
Fever
Irritability/Fussiness
Loss of appetite

Note: parent(s)/LAR(s) will be instructed to measure and record the rectal body temperature in the evening. Should additional temperature measurements be performed at other times of day, parent(s)/LAR(s) will be instructed to record the highest temperature in the diary card.

### 9.1.4. **Clinical laboratory parameters and other abnormal assessments qualifying as adverse events or serious adverse events**

In absence of diagnosis, abnormal laboratory findings (e.g., clinical chemistry, hematology, urinalysis) or other abnormal assessments (e.g., physical examination) that are judged by the investigator to be clinically significant will be recorded as AE or SAE if they meet the definition of an AE or SAE (refer to Sections 9.1.1 and 9.1.2). Clinically significant abnormal laboratory findings or other abnormal assessments that are present at baseline and significantly worsen following the start of the study will also be reported as AEs or SAEs.

The investigator will exercise his or her medical and scientific judgement in deciding whether an abnormal laboratory finding or other abnormal assessment is clinically significant.

### 9.1.5. Adverse events of special interest

#### 9.1.5.1. Spontaneous or excessive bleeding

Subjects' parent(s)/ legally acceptable representative(s) (LAR[s]) will be instructed to contact the investigator/study staff if their child presents symptoms of spontaneous bleeding or easy bruising or if their child develops a rash, within 30 days after either vaccination (Visit 1 and Visit 3), in order to detect any thrombocytopenic petechiae or purpura. The investigator will, based on his/her medical judgment, measure the total blood count and appropriately investigate infants with clinical suspicion of low platelets.

Any episode of spontaneous or excessive bleeding occurring within 30 days after each vaccination should be fully investigated with a full range of hematological tests to identify the underlying cause and reported as an AE of special interest.

#### 9.1.5.2. RSV-LRTI

LRTI associated with RSV infection will be reported as an adverse event of special interest in an expedited manner. These will be detected through the surveillance for RSV-RTI (refer to Section 9.2).

[figure not shown]
To identify RSV-LRTI for the purpose of AE of special interest, the diagnosis should be based on the investigators' clinical judgment taking into account the clinical history, the examination, relevant medical investigations and within 24 hours of results of a locally-available diagnostic test for RSV. Of note the case definition presented in [Table 6](#) is based on a limited set of symptoms and signs and is designed for protocol specified analyses pooled across sites at study conclusion and should not be used for the purpose of reporting RSV-LRTI as an AE of special interest during the trial conduct.

In addition to report these cases as AE of special interest, the investigator should investigate the case according to the procedures for the surveillance of RSV-RTI (refer to Section 9.2) and document it in the eCRF. Of note a nasal swab should be taken for confirmatory and quantitative testing of RSV infection by the sponsor.

### 9.2. Surveillance for RSV-RTI, difficulty in breathing and wheezing episodes

Each subject will be under surveillance for RSV-RTI, difficulty in breathing, and wheezing episodes from the administration of Dose 1 (Visit 1) and will continue until the final visit (Visit 8). Surveillance will be performed via phone or e-mail contacts and assessment visits (refer to [Figure 3](#)). The passive and active surveillance contacts can also be made by/with the person designated by the parent(s)/LAR(s) (e.g., grandparents, nanny) as long as the parent(s)/LAR(s) have given approval.

**The safety of the infant is paramount and for any reported illness, the investigator/study staff should assess the need for any intervention and provide this as part of regular healthcare or instruct/advise the parent(s)/LAR(s) where to obtain this care.**

**Figure 3 Decision tree for passive and active surveillance contacts**

 Active contacts will take place weekly during each RSV season and every month outside the RSV season. Passive phone contacts from the parents/LARs to the investigator will take place when symptoms occur.

 Refer to the SPM for signs and symptoms to be collected.

 RSV-A/B quantitative PCR on all specimens.

 RVP (Multiplex PCR) on all specimens RSV-A/B positive and on all cases of confirmed LRTI according to case definition presented in Table 6.

 For example, in the event that the subject requires urgent medical evaluation and care or has travelled to another location.

 In case of worsening of symptoms, optional sample if the previous specimen was RSV-positive, and mandatory if the previous sample was RSV-negative.

**Refer to APPENDIX D for the symptoms and grading for assessment visits and worsening visits.**

### 9.2.1. Passive surveillance

All subjects' parent(s)/LAR(s) will be instructed to contact investigator/study staff in case of any new or worsened RTI symptoms (cough, runny nose or blocked nose) or in case of any new difficulty in breathing or wheezing. They will be also reminded to record the start date and the end date of the RTI symptoms on the RTI episode card.

- **If there is** any new difficulty in breathing, wheezing or parental concern, the investigator/study staff will schedule an assessment visit as soon as possible (refer to Section 9.2.4), but no later than 24 hours after the phone contact to ensure prompt assessment of the need for medical care.
- **If there is no suspicion** of difficulty in breathing, nor wheezing, nor parental concern, but there are any new symptoms of an RTI (cough, runny nose or blocked nose), the investigator/study staff will schedule an assessment visit as soon as possible (refer to Section 9.2.4), but no later than 72 hours after the phone contact. Performing the visit as soon as possible is important to assess the need for medical care, to ensure that early symptoms are captured, and also to collect an optimal nasal swab for the detection of RSV.
- All passive surveillance contacts will be documented in the eCRF.
- In the event that it is not possible to schedule an assessment visit, which may arise if the family has travelled, then the assessment visit page of the eCRF should be filled in as completely as possible using available medical records.

### 9.2.2. Surveillance for asymptomatic RSV-RTI

- In order to detect asymptomatic RSV-RTI, monthly nasal swabs for analysis at sponsor laboratory will be performed for all subjects during the RSV season who are 'RTI symptom free' within an approximate 30 day period. Upon investigators discretion, the asymptomatic visit may be omitted if a nasal swab has been taken for a potential disease episode in the previous 4 weeks (please refer to the SPM for an example of when to schedule the visit). The asymptomatic nasal swab will be tested by quantitative PCR.
- These nasal swabs may be performed in the subject's home or the investigators clinical facility as appropriate to the circumstances in the judgment of the investigator.
- All surveillance visits for asymptomatic RSV-RTI will be documented in the eCRF.

### 9.2.3. Active surveillance

There will be contact between the investigator/study staff and subject's parent(s)/LAR(s) on a regular basis (weekly during the RSV season and every month outside the RSV season). If there has not been a contact through a clinic visit (i.e., Visits 1, 2, 3, 4, 5, 6\*, 7, 8), a passive surveillance contact (refer to Section 9.2.1), an assessment visit (refer to Section 9.2.4) or a surveillance for asymptomatic RSV infection (refer to Section 9.2.2), then the investigator/study staff will contact the subject's parent(s)/LAR(s). The active surveillance will be performed by phone, mobile phone or e-mail.

\* In countries where *Menveo* or Placebo is used as a comparator, no administration will be performed at Day 121 and therefore in those countries there will be no Visit 6 and it will be administered at the end of the first RSV season at Visit 7 (refer to Table 2 and Table 7).

During each active follow-up contact, the investigator/study staff will:

- Confirm with the subjects' parent(s)/LAR(s), if the subject has developed new RTI symptoms (cough, runny nose or blocked nose) and if he/she has developed any symptoms of difficulty in breathing or wheezing (during and between contacts).
  - **If there is** any new or on-going difficulty in breathing, wheezing or parental concern, the investigator/study staff will schedule an assessment visit as soon as possible (refer to Section 9.2.4), but no later than 24 hours after the contact to ensure prompt assessment of the need for medical care.
  - **If there is no suspicion** of difficulty in breathing, nor wheezing, nor parental concern, but any new symptoms of an RTI (cough, runny nose or blocked nose) are present, the investigator/study staff will schedule an assessment visit as soon as possible (refer to Section 9.2.4), but no later than 72 hours after the contact.
- Performing the visit as soon as possible is important to assess the need for medical care, to ensure that early symptoms are captured, and also to collect a nasal swab for the detection of RSV.
- The investigator/study staff will remind subjects' parent(s)/LAR(s) to record the start date and the end date of the RTI symptoms on the RTI episode card.
- All active surveillance contacts will be documented in the eCRF.
- In the event that it is not possible to schedule an assessment visit, which may arise if the family has travelled, then the assessment visit page of the eCRF should be filled in as completely as possible using available medical records.

#### **9.2.4. Assessment visit**

The purpose of the assessment visit is to objectively document signs and symptoms by an appropriately qualified person (i.e., medical or nursing), provide medical advice and to take a nasal swab for detection of RSV infection.

- Assessment visits may take place in the subject's home, the investigators clinical facility or a medical facility as appropriate to the circumstances in the judgment of the investigator.
- If the reported symptoms are already of a level of severity that urgent care is indicated, the parent(s)/LAR(s) should be redirected to the proper location to receive this care (e.g., Emergency Room) and an assessment visit could be scheduled to take place there at a suitable time.
- During the assessment visit, the investigator/study staff will evaluate the clinical signs and symptoms of the RTI. Signs and symptoms to be recorded in the eCRF are listed in the SPM.
- Oxygen saturation will be measured by pulse oximetry in room air using standardized equipment in preference.
- Specimen for testing of RSV and RVP at a local routine laboratory will be collected for all the subjects who have symptoms of an RTI.
- Nasal swabs for analysis at sponsor laboratory will be collected for all the subjects who have symptoms of an RTI. Note: all subjects experiencing an RSV-LRTI must be reported as an SAE in an expedited manner (refer to Section 9.4).
- Parent(s)/LAR(s) will be instructed to contact the study staff if the severity of the already existing symptoms increases or if the subject develops difficulty in breathing or wheezing and this may lead to a repeat assessment visit upon the judgment of the investigator.
- During subsequent surveillance contacts after an assessment visit, the status and evolution of the case will be followed until case resolution.
- Each assessment visit will be encoded in the eCRF.

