## Risks linked to the investigational RSV vaccine

Although the ChAd155-RSV vaccine is not a FI-RSV vaccine and the risk of ERD is thought to be very low (refer to Section 1.2), this is the first time that this vaccine will be administered to subjects likely to be unexposed to RSV. Consequently, all subjects will be closely monitored by active and passive surveillance for detection of RSV-RTI and wheezing (refer to Section 9.2). All cases of LRTI associated with RSV will be considered as AEs of special interest (refer to Section 9.1.5) and will have to be reported as SAEs (within 24 hours).

IM vaccination commonly precipitates a transient and self-limiting local inflammatory reaction. This may typically include redness, swelling and tenderness.

Most systemic symptoms observed in a clinical trial with a similar product carried out in healthy adults (chimpanzee adenovirus-based vaccine with ChAd3 as vector for vaccination against hepatitis C) at doses to be used in this trial did not exceed mild severity [HCV001 Clinical Study Report, 2011]. Fatigue, headache and malaise were the most commonly reported systemic AEs overall.

In a Phase I clinical trial with a similar simian adenoviral vector-based RSV vaccine with the same insert (PanAd3-RSV) carried out in healthy adults, the most commonly reported AEs concerned injection site reactions. However, a mild non-clinically significant drop in hemoglobin was noted following vaccination without clinical signs and with a reversal towards baseline values over time [RSV001 Interim Study Report, 2014].

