## 9.4. Reporting of serious adverse events and adverse events of special interest

### 9.4.1. Prompt reporting of serious adverse events and adverse events of special interest to GSK Biologicals

SAEs that occur in the time period defined in Section 9.3 will be reported promptly to GSK within the timeframes described in Table 21, once the investigator determines that the event meets the protocol definition of a SAE.

AEs of special interest (RSV-LRTI and spontaneous or excessive bleeding) that occur in the time period defined in Section 9.3 will be reported promptly to GSK within the timeframes described in Table 21.

**Table 21 Timeframes for submitting serious adverse event and adverse events of special interest reports to GSK Biologicals**

Type of Event	Initial Reports		Follow-up of Relevant Information on a Previous Report	
	Timeframe	Documents	Timeframe	Documents
SAEs	24 hours*†	electronic Expedited Adverse Events Report	24 hours*	electronic Expedited Adverse Events Report
AEs of special interest (RSV-LRTI)	24 hours*†	electronic Expedited Adverse Events Report	24 hours*‡	electronic Expedited Adverse Events Report
AE of special interest (spontaneous or excessive bleeding)	24 hours*†	electronic Expedited Adverse Events Report	24 hours*	electronic Expedited Adverse Events Report

\* Timeframe allowed after receipt or awareness of the information.

† The investigator will be required to confirm review of the SAE/ AE of special interest causality by ticking the 'reviewed' box in the electronic Expedited Adverse Events Report within 72 hours of submission of the SAE/ AE of special interest.

‡ In the timeframe of awareness for the local RSV test result.

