**9.4.4. Reporting of adverse events of special interest to GSK Biologicals****9.4.4.1. RSV-LRTI**

**Note that ALL LRTI meeting the criteria of an SAE should be reported as SAEs with the timing of SAE reports.**

In addition, once an investigator becomes aware that an episode of LRTI not meeting the criteria of an SAE, but which has been confirmed on local testing to be due to RSV has occurred in a study subject, the investigator (or designate) must complete the information in the electronic Expedited Adverse Events Report **WITHIN 24 HOURS**. The report will always be completed as thoroughly as possible with all available details of the event. Later additional relevant information is received, the report should be updated **WITHIN 24 HOURS**.

The investigator will always provide an assessment of causality at the time of the initial report. The investigator will be required to confirm the review of causality by ticking the 'reviewed' box in the electronic Expedited Adverse Events Report within 72 hours of submission of the AE of special interest.

Refer to Section 9.4.3.1 for back-up system in case the electronic reporting system does not work.

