## **11. STATISTICAL METHODS**

### **11.1. Primary endpoints**

- Occurrence of adverse events (AEs) from first vaccination (Day 1) up to Day 61.
  - Occurrence of each solicited local and general AE, during a 7-day follow-up period after each vaccination (i.e., the day of vaccination and 6 subsequent days).
  - Occurrence of any unsolicited AE, during a 30-day follow-up period after each vaccination (i.e., the day of vaccination and 29 subsequent days).
  - Occurrence of any serious adverse event (SAE) from Day 1 up to Day 61.
  - Occurrence of episode of spontaneous or excessive bleeding (AE of special interest), during a 30-day follow-up period after each vaccination.

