## 11.2. Secondary endpoints

- Occurrence of RSV-RTI, RSV-LRTI, severe RSV-LRTI and very severe RSV-LRTI (according to standardized case definitions) as from first vaccination (Day 1) up to the end of the first RSV transmission season.
- Occurrence of RSV-RTI, RSV-LRTI, severe RSV-LRTI and very severe RSV-LRTI (according to standardized case definitions) as from first vaccination (Day 1) up to the end of the second RSV transmission season.
- Occurrence of SAEs from first vaccination (Day 1) up to the end of the second RSV transmission season.
- Occurrence of RSV-LRTI (AE of special interest) as from first vaccination (Day 1) up to the end of the first RSV transmission season, and up to the end of the second RSV transmission season.
- Occurrence of very severe RSV-LRTI (according to standardized case definitions) among RSV infected infants with a negative RSV exposure status (at screening based on in-stream baseline serological testing) from first vaccination (Day 1) up to the end of the first RSV transmission season.
- Humoral response to the investigational RSV vaccine, pre-vaccination (Screening), post-Dose 1 (Day 31) and post-Dose 2 (Day 61 and at the end of the first RSV transmission season):
  - Neutralizing antibody titers against RSV-A.
  - RSV F antibody concentrations.

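### The protocol gives two conflicting rules for when an RSV-LRTI is an SAE, so non-serious cases may enter or miss the SAE counts depending on which section a site follows

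*Protocol*

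**What the plan says.** Two places in the protocol make every RSV-LRTI an SAE. Section 9.2.4, on the assessment visit, states that "all subjects experiencing an RSV-LRTI must be reported as an SAE in an expedited manner" and refers the reader to section 9.4. Section 1.3.1, under the risks of the investigational vaccine, calls RSV-associated LRTI an AESI and adds in the same sentence that these cases "will have to be reported as SAEs (within 24 hours").

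Section 9.4.4.1 gives a different rule. It says that "ALL LRTI meeting the criteria of an SAE should be reported as SAEs with the timing of SAE reports", and then describes a second class: "an episode of LRTI not meeting the criteria of an SAE, but which has been confirmed on local testing to be due to RSV". That second class also goes on the expedited report within 24 hours, but as an AESI.

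Other sections agree with 9.4.4.1. Section 9.1.5.2 says that "LRTI associated with RSV infection will be reported as an adverse event of special interest in an expedited manner". Section 1.2.4.1 likewise calls all RSV-LRTI AESIs, to be reported within 24 hours, without calling them SAEs. Section 9.4.1 starts SAE reporting "once the investigator determines that the event meets the protocol definition of a SAE", and its Table 21 has separate rows for SAEs and for RSV-LRTI. The SAE definition in section 9.1.2 rests on outcome (death, threat to life, hospitalization, disability, or an important medical event by judgement) and does not make RSV-LRTI serious by default.

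SAE occurrence is an endpoint twice. Section 11.1 lists "Occurrence of any serious adverse event (SAE) from Day 1 up to Day 61" as primary and section 11.2 lists "Occurrence of SAEs from first vaccination (Day 1) up to the end of the second RSV transmission season" as secondary.

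**The concern.** Take an infant with a positive local RSV test and a raised respiratory rate whom the investigator diagnoses with LRTI, who is not admitted and meets no criterion of section 9.1.2. Under sections 1.3.1 and 9.2.4 this is an SAE. Under section 9.4.4.1 it is an AESI and not an SAE. The class is set by the site when the event is reported, so a later analysis rule may not recover what the site would have done under the other section.

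What is at stake is the meaning of the SAE percentages. If some sites follow 9.2.4 and others 9.4.4.1, the count mixes two definitions. The secondary endpoint, which runs through both seasons, carries most of the effect. The cumulative SAE tables that section 9.10.3 sends to the IDMC each month are affected in the same way. RSV lower respiratory disease is also the event class this trial was built to watch.

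**Working it through.** **Step 1. Compare the rules.**

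| RSV-LRTI case | 1.3.1 and 9.2.4 | 9.4.4.1 (with 9.1.2, 9.1.5.2, 9.4.1) |
|---|---|---|
| Meets an SAE criterion, for example hospitalized | SAE | SAE |
| Locally confirmed, meets no SAE criterion | SAE | AESI only |

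Only the second row differs. If every RSV-LRTI were an SAE, the second class in 9.4.4.1 would be empty, so the two rules cannot both hold. All of this is current text, not the amendment log.

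**Step 2. Reproduce the protocol's own SAE figure.** Section 11.4 gives about 92% as the probability of at least one SAE among 50 infants when the true rate is 5%. The exact binomial value is 1 − 0.95^50 = 0.923, which agrees. The dispute is not about this figure; it supplies a reference rate.

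**Step 3. Illustrate the size.** Inputs:
- group size 50 (section 11.4);
- first-season infection rate 20% (section 11.4);
- hypothetical SAE rate 5% under the 9.4.4.1 rule (section 11.4);
- q, the share of infections that are non-serious RSV-LRTI. The protocol gives no value, so q = 10% to 50% is assumed, independent of the other SAEs.

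Infants per group whose status changes: 50 × 0.20 × q = 10q.

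Share with at least one SAE if every site follows 9.2.4: 0.05 + 0.95 × 0.20 × q.

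| q | Infants changing status per 50 | Share with an SAE | Expected infants with an SAE per 50 | P(at least one SAE in 50) |
|---|---|---|---|---|
| 0 (9.4.4.1 rule) | 0 | 5.0% | 2.50 | 92.3% |
| 10% | 1 | 6.9% | 3.45 | 97.2% |
| 20% | 2 | 8.8% | 4.40 | 99.0% |
| 30% | 3 | 10.7% | 5.35 | 99.65% |
| 50% | 5 | 14.5% | 7.25 | 99.96% |

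The ratio to 5.0% runs from 6.9/5.0 = 1.4 to 14.5/5.0 = 2.9.

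Two cautions apply. Section 11.4 uses the 20% for infants with a negative RSV exposure status, whereas the SAE analysis covers the whole Exposed Set; applying it to all 50 is part of the illustration. If only the exposure-negative half were infected, the count would be 50 × 0.5 × 0.20 × q, or 0.5 to 2.5 infants. The calculation also covers one season, while the secondary endpoint covers two.

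**Step 4. Locate the effect in time.** The primary SAE endpoint closes at Day 61. Section 7.3 requires Dose 1 before the first RSV season, so much of a season's RSV-LRTI should come after Day 61. Some may fall earlier, because Day 61 can lie inside the season. The protocol gives no basis for a figure in that window.

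**The case against.** The strongest reply is that the protocol shows which rule governs. The sentence in 9.2.4 is a note that sends the reader to section 9.4, where the reporting instructions are, and 9.4.4.1 states the two-class rule plainly. The text in 1.3.1 is background and itself calls these events AESIs. Both classes use the same expedited form within 24 hours, so being reported as an SAE could mean only the reporting route. This narrows the conflict without removing it. Section 9.2.4 says the case must be reported as an SAE, is the instruction staff use at the visit, and does not limit itself to the route. Section 9.4.4.1 gives non-serious cases the same form without calling them SAEs.

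It is also right that little else depends on the class. RSV-LRTI goes to the iSRC and the IDMC within 48 hours either way, holding rule 2d counts hospitalizations, and the Table 6 and AESI endpoints stand. The SAE analysis is descriptive.

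Some stronger readings are tempting and are not supported:
- **All RSV-LRTI change status.** Taking 150 × 20% = 30 infections and an assumed 20% to 50% with LRTI gives 6 to 15 cases, but serious cases are SAEs under both rules. Only the non-serious remainder moves.
- **SAE counts double or triple.** That needs the upper part of an assumed range and every site following 9.2.4. The 5% reference is itself hypothetical.
- **Events are counted twice.** SAE and AESI tables overlap by design, and a hospitalized RSV-LRTI belongs in both under either rule.
- **True seriousness is hidden.** Severe and very severe RSV-LRTI and RSV hospitalization are separate categories in Table 6, and Appendix D records admission, oxygen, ventilation and intensive care.
- **The groups are biased against each other.** Randomization balances the groups within country, so differences in practice between countries should fall about equally on them.

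**Conclusion.** The contradiction stands: sections 1.3.1 and 9.2.4 are wrong as written when set against 9.4.4.1 and the sections that support it. This is an internal inconsistency, not a design choice. Its consequence is limited to which non-serious RSV-LRTI enter the SAE counts, chiefly in the secondary endpoint to the end of the second season and in the IDMC's cumulative SAE tables, and less so in the Day 61 primary endpoint.

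The illustrated size, 1 to 5 infants per group of 50, rests on the assumed 10% to 50% share and on the 20% infection rate applied to a whole group. The move from 5.0% to between 6.9% and 14.5% also needs the hypothetical 5% reference and uniform use of 9.2.4. Mixed practice would give something in between. The textual conflict does not depend on any of these figures.

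**What to change.** Reconcile the sentence in section 1.3.1 and the note in section 9.2.4 with section 9.4.4.1. Both should say that every locally confirmed RSV-LRTI is reported within 24 hours as an AE of special interest, and is classed as an SAE only when a criterion of section 9.1.2 is met. Send sites a short reminder of the rule.

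The cost is two sentences in an amendment plus the reminder. Expedited reporting, iSRC and IDMC notification, the holding rules and the RSV disease endpoints stay as they are.
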